- To evaluate side effects or adverse events of gabapentin in this setting
- To identify subgroups where adjunctive gabapentin may be more effective at reducing perioperative pain such as gestational age ranges and patient characteristics (age, gravidity, substance abuse, preoperative anxiety level).

Background and Rationale:

Surgical abortions in North America are typically performed using either local anesthetic with oral analgesics or moderate sedation. A 2009 Cochrane review of evidence for pain control assessed that paracervical block in reducing abortion related pain is limited, while the addition of ibuprofen and naproxen can slightly reduce intraoperative and post operative pain [6]. Evidence supports the benefit of conscious sedation at reducing intraoperative and post-operative pain in abortions [7]. General anesthesia can be useful in some settings, however its use is limited due to cost, staffing and potential for additional risks. Further, studies have found, although better at reducing pain during the procedure, general anesthesia is not superior to moderate sedation for post-operative pain [8]. Other recently examined adjuncts to pain control have not proven to be beneficial in this setting [9-11].

Gabapentin is widely used to treat neuropathic and chronic pain. Mechanism of action may include calcium channel blockade and modulation of nociceptive neurotransmitters. Clinical trials support use of perioperative pregabalin and gabapentin to reduce perioperative and post-operative pain in a variety of clinical settings, for both major and minor surgical procedures [2, 12]. While pregabalin has a faster peak plasma concentration, gabapentin is a less expensive option with peak concentrations reached by 2 hours, with substantial evidence to support routine use and safety in reducing perioperative pain. In a systematic review of 22 randomized controlled trials (RCT), a single preoperative dose of gabapentin significantly reduced 24-hour

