600 mg of gabapentin was selected as a well-tolerated intermediate dosage with benefit proven in prior perioperative pain studies. The window of 1-2 hours is consistent with preoperative dosing in other studies and can allow for its co-administration with misoprostol, and allows for some variability that is practical with a busy clinic.

Study Procedures:

All recruitment, screening and enrollment questions will be asked by trained study staff in a private room.

Recruitment:

We will be recruiting a total of 96 women, with equal allocation to the invention group and placebo. The proposed research will take place at Duke Ryan Clinic, at the Duke gynecology outpatient clinic. Women who attend Duke for a uterine aspiration will have their preoperative evaluation and over the phone counseling. During this call, the clinical provider will introduce the study to the patient to determine interest in participating in the study. All patients are scheduled and given standardized pre-procedure counseling by our clinic coordinator. If the patient is interested in possible participation, study personnel will be notified. The study team will then contact the patient to provide them with information about the study. A standard recruitment script will be employed (Appendix A).

Screening and consent:

For individuals who are interested in participating, we will screen for eligibility using an eligibility checklist (Appendix A). Those eligible after screening will review the informed consent and sign consent forms prior to the final clinical preoperative review. Patient contact information will be collected at this time. After the nurse reviews the medical chart, randomization will occur and intervention will be received.

Randomization, Allocation Method and Blinding:

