Randomization to study method will occur after completion of all intake forms and consent, immediately before the pill is to be taken, thus reducing the possibility of withdrawal after randomization. Primary outcome measures and most secondary outcome measures will be assessed immediately before, during or after the abortion procedure, thus any loss to follow-up will be limited to those who consent to, but change their mind while waiting for their procedure. Based on current clinical practice at this clinic, withdrawal after consent is extremely rare. Our secondary outcomes assessed post-operatively after discharge will be collected via the phone. We will maximize completion of these assessments through the following steps: participants will be told beforehand about the telephone contact following the procedure, a cellular telephone number will be collected and tested at the clinic, a secondary phone number and email will be collected as a backup, participants will be given a contact number for the study coordinator should they have any challenges with receiving a phone calls, and participants will receive an additional \$10 sent to their gift-card following the completion of their phone assessment.

Data Collection/Outcome measurements:

Outcome measures and baseline variables are described in Table 1.

Primary study outcome

Our primary outcome measure will be pain score using an 100-mm visual analog scale (VAS) measured 5 minutes after removal of the speculum.

Secondary Outcomes:

We will also be measuring pain on the 100-mm VAS preoperatively immediately prior to the procedure, after the procedure, 10 minutes and 30 minutes following the procedure and at discharge. Nausea, using a VAS, and vomiting will be assessed preoperatively immediately prior to the procedure and post operatively at 10 minutes, 30 minutes and at discharge. Anxiety prior to the procedure will be measured using the preoperative state trait anxiety inventory. Side effects will be assessed using a checklist prior to discharge. We will also be contacting participants on post-operative day 1 to assess pain, nausea, vomiting, side effects and general satisfaction with the procedure (on a 5-point scale). The quantity and type of medications used perioperatively and post-operatively including medications used at home in the 24 hours post-operatively will be abstracted from the clinical record and assessed on the phone.

Baseline Characteristics and covariates:

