We will collect baseline demographics, medical history (gravidity, parity, prior abortions (medical and surgical), gestational age, drug and alcohol use, psychiatric or sexual assault history), medications used at home and given at the clinic preoperatively, indication for procedure (personal/social, fetal or maternal health)).

Study Size and Power:

We will enroll a total of 96 women. Assuming a standard deviation of 26 mm on the 100-mm visual analog scale (VAS), based on prior studies, this will provide us with an 80% power, using a p-value of 0.05, to detect a 15 point difference in pain among all participants. A difference of 15-20 mm has been assessed to be clinically meaningful in prior studies. Given that our primary outcome will be measured immediately after the procedure, our loss to follow-up will be minimal. A 100-mm pain visual analog scale has been shown to be useful for the evaluation of pain in prior pain abortion research [5, 6] with a mean standard deviation in previous studies of approximately 26 mm [5]. We are assuming no loss-to-follow-up as our primary outcome will be measured at the time of the procedure.

Data Management and Analysis

Data Management:

Prior to study initiation, a database will be developed using a web-based password-protected relational database (REDCap). All data will be collected will be recorded on clinical research forms (CRFs) and entered into the database at the end of each day. All CRF source documents will be filed and stored for future reference. See monitoring and oversight section below for further details on procedures and protections.

Analytic Plan:

We will compare groups on the primary continuous outcome measure (pain score on 11-point VAS) using T-tests. Chi-square and T-tests will be used to evaluate secondary outcomes for categorical and continuous variables, respectively. Baseline characteristics will be evaluated for potential interaction or confounding with primary and secondary outcomes.

Upon study completion at each site for the prospective meta-analysis, data from each site will contribute to the final meta-analysis using criteria outlined in the Cochrane Handbook for Systematic Reviews of Interventions. Site RCT publications will mention contribution to this PMA. Subgroup analyses will address gabapentin adjunct to local anesthesia and moderate sedation, as well as by specified population characteristics and gestational age.

Ethical Concerns

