ANXIOUS**4. Make a hash mark on the line to indicate how much nausea you are currently experiencing.**NO
NAUSEA _____WORST NAUSEA
I HAVE EVER HAD5. Have you vomited since you had your procedure? ₀ NO ₁ YES

SIDE EFFECTS: Do you have any of the following?

Dizziness	 ₀ NO  ₁ YES, mild  ₂ YES, moderate  ₃ YES, severe
Ataxia (lack of muscle control)	 ₀ NO  ₁ YES, mild  ₂ YES, moderate  ₃ YES, severe
Somnolence (sleepiness or drowsiness)	 ₀ NO  ₁ YES, mild  ₂ YES, moderate  ₃ YES, severe
Asthenia (weakness, lack of energy)	 ₀ NO  ₁ YES, mild  ₂ YES, moderate  ₃ YES, severe
Headache	 ₀ NO  ₁ YES, mild  ₂ YES, moderate  ₃ YES, severe
Amblyopia (vision in one eye reduced/lazy eye)	 ₀ NO  ₁ YES, mild  ₂ YES, moderate  ₃ YES, severe

Post- anesthetic alдрete recovery score : modified Criteria	Points
Oxygenation	
SpO ₂ > 92% on room air	2
SpO ₂ > 90% on oxygen	1
SpO ₂ < 90% on oxygen	0
Respiration	
Breathes deeply and coughs freely	2
Dyspneic, shallow or limited breathing	1
Apnea	0
Circulation	
BP +/- 20% of normal	2
BP +/- 20-50% of normal	1
BP > 50% of normal	0
Consciousness	
Fully awake	2
Arousable on calling	1
Not responsive	0
Activity	
Moves all extremities	2
Moves two extremities	1
No movement	0

30-Minute Post Op Assessment

Time: ____ : ____ AM/PM

1. Make a hash mark on the line to indicate the worst pain you have felt up to this point today.NO
PAIN _____WORST PAIN
IN MY LIFE**2. Make a hash mark on the line to indicate how much pain you are currently in.**NO
PAIN _____WORST PAIN
IN MY LIFE**3. Make a hash mark on the line to indicate how much anxiety you are currently experiencing.**NO
ANXIETY _____EXTREMELY
ANXIOUS**4. Make a hash mark on the line to indicate how much nausea you are currently experiencing.**NO
NAUSEA _____WORST NAUSEA
I HAVE EVER HAD

4. Have you vomited since you had your procedure?

 ₀ NO ₁ YES

Discharge Assessment

Time: ____ : ____ AM/PM

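### The coding and test for the ordered 0–3 side-effect grades are not specified; if chi-square is run on the four grades, severity order is ignored and power is usually lost

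*Combined protocol and SAP*

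**What the plan says.** - Secondary Aims list the harm question: "To evaluate side effects or adverse events of gabapentin in this setting".
- Data Collection/Outcome measurements, Secondary Outcomes, gives the method of collection: "Side effects will be assessed using a checklist prior to discharge". It gives no grading, no cut-point and no expected rate.
- The Draft Questionnaire, 10-Minute Post Op Assessment, introduces the checklist with "SIDE EFFECTS: Do you have any of the following". It lists six symptoms (dizziness, ataxia, somnolence, asthenia, headache, amblyopia). Each has four ordered answers coded 0 (no), 1 (mild), 2 (moderate) and 3 (severe).
- Data Management and Analysis, Analytic Plan, assigns the tests: "Chi-square and T-tests will be used to evaluate secondary outcomes for categorical and continuous variables, respectively". It does not mention side effects by name, and it names no rank, trend, ordinal or exact test and no rule for sparse tables.
- Study Size and Power: "We will enroll a total of 96 women". The Recruitment section specifies equal allocation, so 48 per arm. The 80% power stated there is for the VAS pain score only.

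**The concern.** The form collects severity, but the analysis sentence has nothing that uses it. Read at face value, a four-level graded outcome is categorical and goes to chi-square. A Pearson chi-square on a 2×4 table spends three degrees of freedom and returns the same p-value if the columns are shuffled. A move from mild to severe therefore counts no differently from any other rearrangement.

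This is a harm comparison, and the introduction hypothesises few adverse effects. A less sensitive test on harm leans towards finding no difference, which is the result the hypothesis predicts. The open coding adds a second problem. The cut (any, or moderate-or-severe) could be chosen after the allocation is revealed, and a harm endpoint left undefined is harder to pool in the planned prospective meta-analysis.

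**Working it through.** **The plan's own figure.** The only stated power is for pain: 15 mm difference, SD 26 mm, alpha 0.05 (two-sided assumed). n per arm = 2 × (1.960 + 0.842)² × 26² / 15² = 2 × 7.849 × 676 / 225 = 47.2, so 48. Power at 48 per arm is 80.7% by the normal approximation and 79.9% by the t distribution. The figure reproduces, but it says nothing about side effects.

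**Inputs for side effects.** From the documents: 48 per arm, four ordered grades, alpha 0.05. The documents give no side-effect rates or effect sizes, so these are assumed: seven placebo grade distributions, from 90% reporting none down to 25% in each grade, and a common (proportional) odds ratio of 1.5 to 5.

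**How a shift is built.** The odds of being at or above each grade are multiplied by the odds ratio. Example: placebo 70/20/8/2%, odds ratio 2.5.
- At least mild: 0.30/0.70 = 0.4286; × 2.5 = 1.0714; probability 0.517.
- At least moderate: 0.10/0.90 = 0.1111; × 2.5 = 0.2778; probability 0.217.
- Severe: 0.02/0.98 = 0.0204; × 2.5 = 0.0510; probability 0.049.
- Gabapentin arm: 48.3/30.0/16.9/4.9%.

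**Simulated power** (20,000 trials per scenario; rank-sum is tie-corrected):

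| Placebo none/mild/mod/severe, % | Odds ratio | 2×4 chi-square | Any-v-none chi-square | Rank-sum |
|---|---|---|---|---|
| 50/30/15/5 | 1.5 | 11.6% | 16.8% | 18.5% |
| 50/30/15/5 | 2.5 | 50.1% | 57.5% | 67.2% |
| 50/30/15/5 | 5 | 95.9% | 95.1% | 99.0% |
| 60/25/10/5 | 2.5 | 48.1% | 61.3% | 66.3% |
| 70/20/8/2 | 2.5 | 43.2% | 58.7% | 61.6% |
| 80/14/5/1 | 2.5 | 34.9% | 52.5% | 52.4% |
| 90/7/2/1 | 3 | 29.2% | 50.4% | 49.4% |

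**Gap, rank-sum minus 2×4 chi-square**, over all seven distributions: 5–7 points at odds ratio 1.5, 11–15 at 2, 16–18 at 2.5, 15–20 at 3, 7–20 at 4 and 3–16 at 5. An analytic check agrees in size: a signal giving 80% power on 1 degree of freedom (noncentrality 7.849) gives 64% on 3, a loss of about 16 points.

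**Gap if the grades are collapsed to any versus none**: about 0–5 points when 60–80% of placebo women report none, and up to about 10 at 50%. It is larger if symptoms are commoner still.

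**Sparse cells.** With equal arms the expected count is half the column total, so it falls below 5 when fewer than 10 of the 96 women choose a grade. In the worked example the expected number of severe answers across both arms is 48 × (0.020 + 0.049) = 3.3. At least one expected count was below 5 in 59–100% of simulated trials when 50–90% of placebo women report none and the odds ratio is at most 3. In those distributions the type I error of the 2×4 test was 2.5–4.4%, so it is conservative. Where symptoms are common in every grade, sparse cells are not a problem.

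**Shifts that are not proportional.** In four such patterns the 2×4 chi-square had 11 to 52 points more power than the rank-sum test:

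| Placebo → gabapentin, % | 2×4 chi-square | Rank-sum | Any v none | Moderate-or-severe v less |
|---|---|---|---|---|
| 60/25/10/5 → 35/50/10/5 | 61.5% | 50.5% | 70.4% | 5.6% |
| 60/25/10/5 → 60/10/10/20 | 63.2% | 10.9% | 5.1% | 42.3% |
| 50/30/15/5 → 30/55/13/2 | 56.1% | 23.3% | 52.0% | 10.2% |
| 60/30/8/2 → 50/20/20/10 | 54.2% | 37.7% | 16.9% | 71.4% |

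In the second and fourth rows severity rises among women with symptoms. The rank test does poorly there, and a moderate-or-severe comparison recovers much of the signal.

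**The case against.** The strongest reply is that nothing in the plan says a 2×4 table will be tested. The Analytic Plan does not mention side effects, the outcomes section speaks only of a checklist, and the form offers a no and three kinds of yes. Any versus none fits that text as well, and chi-square is then a sensible test with little power lost for symptoms most placebo women do not report. This stands: the 2×4 loss is conditional. It does not close the point, because any versus none is not stated either. It also cannot see a move from mild to severe, as the 5.1% above shows.

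A reader might infer that the plan forfeits a fixed 17–18 points of power. The documents do not support that. The figure appears near an odds ratio of 2.5 under proportional odds in a four-grade table, is close to the largest loss found, and rests on rates the documents never give.

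A reader might also extend the point to satisfaction. That is not supported. The outcomes section describes "general satisfaction with the procedure (on a 5-point scale"), while the 24-hour form uses 0 to 10, and an 11-level score could well go to the t-test, which does use order.

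Other mitigations are fair. Chi-square does not inflate false positives here, side effects have no power target, and the primary analysis is untouched. A medical monitor and a Data Monitoring Committee also review safety, and the form is labelled a draft. These limit the weight of the point, but they do not tell the analyst how to compare the grades.

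**Conclusion.** The point holds as a gap in specification with a conditional cost in power. The grades are ordered, the only test named for categorical secondary outcomes ignores order, and no coding is given. If the four grades are tested as they stand, the cost against a consistent shift is roughly 3–20 points (48 per arm, two-sided 0.05, assumed grade distributions, proportional odds ratio 1.5–5). If they are collapsed to any versus none, it is about 0–5 points with 60–80% of placebo women at none and up to about 10 at 50%. For non-proportional shifts the rank test can be the weaker one. None of these sizes is a property of the plan, because the documents give no side-effect rates. The matter is worth correcting because side effects are a stated aim and the correction is nearly free, but it threatens neither the primary result nor the type I error.

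**What to change.** In the Analytic Plan:

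1. State that each side effect is analysed on its 0–3 grade with a Wilcoxon rank-sum test, or with a proportional-odds model reporting the common odds ratio and 95% CI.
2. For each side effect, also report the risk difference with 95% CI for moderate-or-severe grades, so that a shift in severity among symptomatic women is visible.
3. Keep chi-square for yes/no outcomes such as vomiting, with an exact test where an expected count is below 5.
4. Separately, reconcile the satisfaction scale between Secondary Outcomes (5 points) and the 24-hour form (0–10).

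The cost is a few sentences, fixed before the allocation is revealed, with no new data and no change to sample size. The downside is that rank and proportional-odds tests are less sensitive to non-monotone patterns. The moderate-or-severe estimate covers part of that, but not a rise confined to mild symptoms.

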Women undergoing a procedure who meet study inclusion criteria and complete informed consent will be eligible for participation. *Randomization* will be done using computer-generated random numbers (randomization.com) in variable blocks of 8 and 10. *Allocation* concealment will be maintained by identically labeled sealed sequentially numbered opaque pill containers. Gabapentin and placebo tablets will be indistinguishable by appearance, thus maintaining blinding for participants and assessors. To maintain double *blinding* for both investigators and participants, an individual not associated with study conduct will create the randomization sequence and allocation containers. The randomization assignments will only be revealed at the point of data analysis or if an interim assessment is needed.

Enrollment:

After the final perioperative clearance, the individual will be randomized and receive their method allocated by the clinic nurse. The study staff will review the enrollment questionnaire that includes demographic questions. Following completion of the questionnaire, the participant will wait before moving to our procedure room (this will occur approximately 1-2 hour after nursing review and receipt of the study intervention). Prior to initiating the procedure, study staff will administer the preoperative questions. The physician will then complete the uterine aspiration while the study staff remains outside of the operative room. Immediately following the procedure, the study staff will then administer the immediate post-operative questions and follow the participant to the recovery room to complete the remaining questions assessed at 5 minutes, 10 minutes, 30 minutes and at discharge. When the discharge questions are complete, the

participant will receive a \$20 gift card and instructed to expect a follow-up call the following day.

Follow-up:

On the day following the procedure (approximately 24 hours after the procedure), study staff will call the participant to complete the follow-up questions. On completion of the questions, an additional \$10 will be transferred to the gift card.

Withdrawals, losses and deviations:

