An adverse event (AE) is defined as any health-related reaction, effect, toxicity or abnormal laboratory result that a study participant experiences during the course of the study, irrespective of relationship to the study intervention. This includes changes in a participant's condition that have or could have a deleterious effect on a participant's health or well-being. A serious adverse event (SAE) is defined as any experience that is fatal or life-threatening, requires

in-patient hospitalization or prolongation of an existing hospitalization, or results in a persistent or significant disability or incapacity.

This study uses an additional medication for pain control in the setting of outpatient abortion. These activities are not anticipated to be associated with any deleterious impact on participants' health or well-being beyond the risks associated with the abortion procedure. AEs will be managed according to good clinical practice and the judgment of the on-site physician. All clinical and laboratory AEs will be followed-up closely by study staff. Any SAEs will be expeditiously reported to the principal investigators, via a designated SAE form. Notification and submission of SAE forms should occur within 48 hours of the site awareness of the SAE. The PI will then make the final independent judgment as to the severity, relatedness, and anticipated or unanticipated nature of the SAE and finalize the Human Subjects Adverse Event Report Form. If the event is determined to be serious, unanticipated, and the relationship is anything other than probably or definitely not related, then the PI will report the event within 48 hours and submit the required forms to the IRB at Duke. Thus, all anticipated SAEs that are at least possibly related to study intervention and all deaths that are at least possibly related to study intervention will be submitted to the Duke IRB.

The study may be discontinued at any time by an IRB at a participating institution or the Office for Human Research Protection. We will additionally have a medical monitor to review any adverse event and periodically review side effects to see if there are an increased number of events than anticipated by routine clinical care. If any suspicion for increased risk exists, study allocation may be revealed for a preliminary analysis and if related to the study intervention, the study could be prematurely ended.

Data Monitoring Committee/Study Termination

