A Data Monitoring Committee (DMC) will be created to perform regular and timely review of data in order to identify early, significant benefit or harm for patients while the trial is in progress. On a regular basis (frequency as to be determined by the DMC based on the enrollment rate and potential risk to subjects), non-identified safety data will be communicated to the DMC who will then meet to review the data. The DMC will be composed of three faculty members within the Duke University Department of Gynecology and Obstetrics. Individuals who are investigators or co-investigators cannot be members. Members must have no financial,

scientific, or other conflicts of interest with the study. All investigators understand that the DMC serves as additional human subject's protection, but does not supplant reporting of significant adverse events to the Duke IRB. The DMC may devise its own stopping rules, and if there are significant numbers of adverse events, the DMC will recommend continuation, modification, or termination of the study after each meeting. This recommendation will be communicated to the Principle investigator who is responsible for reviewing the recommendation and forwarding it to the IRB. All investigators understand that the DMC may recommend their own "stopping rule" if other events occur which indicate a significant risk to study subjects.

Innovation

Gabapentin is a safe and inexpensive medication that has been employed as an adjunct to anesthesia with significant reductions in peri-operative pain and nausea. We aim to explore this novel medication as an adjunct to pain management strategies where other interventions have been less successful in improving pain scores. Further, we will employ the prospective meta-analysis design to increase the power, generalizability and capacity for evaluating sub-group interactions to gain a broader definitive understanding of the use of gabapentin in outpatient abortion care.

Strengths and Weaknesses, Limitations and Future directions

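### Does the DMC's remit to find early benefit inflate the 5% error rate of the final pain comparison?

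*Combined protocol and SAP*

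**What the plan says.** The section Data Monitoring Committee/Study Termination gives the committee's purpose as regular review "in order to identify early, significant benefit or harm for patients while the trial is in progress". The committee sets the frequency of its meetings. The next step in the same paragraph is that "non-identified safety data will be communicated to the DMC who will then meet to review the data". Later the paragraph says "The DMC may devise its own stopping rules". That sentence goes on to make the committee's recommendation depend on the number of adverse events, and a second mention of a stopping rule refers to events that point to significant risk for participants.

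Study Size and Power says of the 96 women that "this will provide us with an 80% power, using a p-value of 0.05, to detect a 15 point difference in pain". The Analytic Plan has one comparison of the primary pain score, by t-test. Neither section mentions an interim analysis, a boundary or a reduced final significance level.

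Two other places allow allocation to be opened before the end. Randomization, Allocation Method and Blinding says "The randomization assignments will only be revealed at the point of data analysis or if an interim assessment is needed". Adverse events says that "study allocation may be revealed for a preliminary analysis and if related to the study intervention, the study could be prematurely ended", on the condition that an increased risk is suspected.

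**The concern.** A committee told to look for significant benefit, at meetings it schedules itself and with rules it writes itself, could in principle test the pain score several times. The final test uses the whole 0.05, so nothing is held back for those looks. Repeated testing at an unadjusted threshold raises the chance of a false positive. A trial stopped early on a favourable fluctuation also tends to overstate the effect, and this site's estimate is to enter a prospective meta-analysis.

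The unblinding sentences add to the unease. The interim assessment is not defined, and neither passage says who would see the allocation. The primary outcome is a self-reported pain score, which depends on participants and assessors staying blind.

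**Working it through.** **1. The plan's own figure.** Inputs from Study Size and Power: difference 15 mm, SD 26 mm, power 80%, significance level 0.05. Sidedness is not stated; two-sided is assumed.

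n per arm = 2 × (1.960 + 0.842)² × 26² / 15² = 2 × 7.85 × 3.004 = 47.2, rounded up to 48, so 96 in total.

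Power at 48 per arm: the standard error is 26 × √(2/48) = 5.31 mm, and 15/5.31 = 2.83. Power is Φ(2.83 − 1.96) = 80.7%, or 79.9% with the noncentral t. A one-sided test would need 38 per arm, 76 in total. The stated 96 therefore matches a single two-sided test at the full 0.05, with nothing set aside for interim looks.

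**2. What repeated testing would cost.** The plan gives no number of looks and no threshold, so both are assumed here: K equally spaced analyses including the final one, each at two-sided p<0.05, with stopping on significance. The overall error is 1 − P(|Z₁|<1.96, …, |Z_K|<1.96), where the correlation between analyses j and k (j<k) is √(j/k). It was obtained by numerical integration. Simulated t-tests with 48 per arm agreed for up to four analyses. By symmetry, false claims of benefit are half the two-sided rate.

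| Analyses, final included | Two-sided error | False claims of benefit |
|---|---|---|
| 1 | 5.0% | 2.5% |
| 2 | 8.3% | 4.2% |
| 3 | 10.7% | 5.4% |
| 4 | 12.6% | 6.3% |
| 5 | 14.2% | 7.1% |

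The threshold matters as much as the number of looks. With p<0.001 at each interim and 0.05 at the end, the two-sided rate is 5.0% to 5.1% for two to five analyses.

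**3. Which row the plan is in.** Four elements would be needed for any row below the first:

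- *Pain data sent to the committee.* The section names only safety data.
- *A scheduled interim test of pain.* None appears in any section; the Analytic Plan has one comparison.
- *A rule for stopping on benefit.* None is given. The action described in the DMC section depends on adverse events or risk to participants.
- *Allocation opened to assess benefit.* The only circumstance described is suspected increased risk, in Adverse events.

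None of the four is present, so the first row applies: one test, 5.0%.

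**4. The unblinding gap.** The Adverse events section describes one kind of early look, a safety analysis after suspected increased risk. That is the natural meaning of the interim assessment in the blinding section. It is introduced together with the medical monitor's review. The DMC excludes investigators and co-investigators, and what it passes to the principal investigator is a recommendation. The randomization sequence is created by someone outside the conduct of the study. The documents do not name the recipient of unblinded group results, but these arrangements point to the medical monitor or the committee.

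**The case for a change.** The strongest case for acting is that the text contradicts itself. A committee cannot find significant benefit from safety data alone, so either the purpose or the data flow is misdescribed. The committee may also write its own rules, and nothing expressly forbids it to ask for pain scores. Two or three sentences would settle the matter without touching the sample size, and the missing statement on who sees allocation matters for a subjective outcome even if no benefit test is ever run.

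Much of this stands. The benefit wording does not fit the rest of its paragraph, the interim assessment is undefined, the recipient of unblinded results is not named, and the arithmetic on repeated looks is right for its assumptions. What does not stand is the step to an inflated primary test. It needs data the committee is not sent, a test nobody has scheduled and an unadjusted threshold that appears nowhere. The concern about the meta-analysis depends on the same unplanned early stop. The low cost of clarification does not turn a drafting inconsistency into a defect of the analysis.

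**Conclusion.** No change to the plan follows. Under the data flow and triggers actually described, pain is compared once, at the end, at 0.05; the 96 women and roughly 80% power are unaffected. The 8.3% to 14.2% range belongs to a procedure that the plan does not contain.

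What remains is a loose phrase about the committee's purpose and two missing details about interim unblinding. Analysts can read these sensibly: safety review only, no between-arm comparison of pain before the final analysis, and unblinded group results kept away from investigators and assessors. That reading changes no planned analysis or result.

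The conclusion assumes that the committee receives what the plan says it receives. If the committee were in fact given pain scores by arm and allowed to stop for benefit, the table above would apply and a pre-specified boundary would be needed.
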